Our primary hypothesis is that there is no difference in cosmetic outcomes between suture repair and conservative treatment of simple, superficial (<2cm) hand and feet lacerations in the pediatric population. Secondary measures will be infection rates, pain scores, time to return to normal activity, time of initial ED visit, and cost of supplies used in repair. Our aim is to show that conservative repair saves time, money and reduces patient pain compared to traditional suture repair, while having no decrease in cosmetic satisfaction or infection rates.

Please save frequently

c) Describe the study design (e.g., single/double blind, parallel, crossover, control, experimental, observational, etc.). If the study is investigator-initiated, a timeline for individual subject recruitment, follow-up, and analysis for the study is required. Also, indicate if the subjects will be randomized.

We will use a prospective clinical trial with computer generated randomization to test our hypothesis. Patients will be recruited by a qualified pediatric emergency physician. Once consent is obtained from the parent(s)/legal guardians, patient data will be collected. The patient will have their hand or foot laceration(s) treated in the emergency department at that time by an attending physician, PEM fellow, or senior resident. The patient will then follow-up in 10-14 days for a wound check and satisfaction survey, and then again at 3-4 months for repeat survey and photograph of the healed wound. Our timeline for recruitment is approximately 15-18 months, 12-15m for recruitment, plus 3 months for additional follow-up visits. Analysis of the data should take an additional month.

Protocol Title: Conservative versus Suture Repair of Hand and Feet Lacerations in Children

d) If subjects will be given placebo, please justify placebo use. *?HELP?*

There will be no placebos used in this study.

3. Study Procedures

a) N Is this project a multicenter study (i.e., same project is conducted elsewhere by a different investigator) OR does this study involve conduct of research at multiple sites? Is SLU acting as a coordinating center for other sites OR is the SLU PI a direct recipient of a federal grant for this research? If yes, complete and attach the Supplemental Application for Coordinating Center Activities.
Will the SLU site be participating in all parts/procedures/arms of the study?
If No, explain what SLU will NOT participate in:

Please save frequently

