Patients will be asked to follow-up in the Pediatric Emergency Department in 10-14 days. The patients will have a reminder phone call on day 6-8 for their follow-up visit and arrange for an appointment time. The wounds will be evaluated for complications that were defined a priori as follows: "wound infection" was one that required systemic antibiotics as determined by the treating attending physician; and "wound dehiscence" as a wound that required the placement

Protocol Title:

Conservative versus Suture Repair of Hand and Feet Lacerations in Children

of additional sutures or tissue adhesives. Children in the suture repair group will have their sutures removed. Parents will fill out a follow-up survey at this visit (see Initial Follow-up Survey).

Follow up data will be obtained from the parent or care giver for all subjects in the form of a questionnaire, patient with healing laceration will return with the parent or guardian for inspection of the wound with possible suture removal at 10-14 days then a re-evaluation of the healing wound with digital pictures taken at 3-4 months post ED enrollment for both treatment groups.

Patients will be asked to follow-up in the Pediatric Emergency Department in 12-16 weeks from the initial presentation. The patient will have a reminder phone call in week 11 for this visit and arrangement with time. The parent will fill out a second survey (see Final Follow-up Survey). Photographs of the wound will be taken, using a standardized protocol with a dedicated digital camera, and then printed by a pre-assigned printer. These photographs will be loaded to a computer to prevent alterations.

The photographs will be rated by 3 pediatric emergency physicians on the research team blinded to the treatment assignments. Independent evaluations will enable us to assess inter-observer reliability. The previously validated Visual Analogue Scale (VAS) will be used to assess the cosmetic outcome. The frequently used scale is a 100mm continuous line that is marked on the right end with "best scar" and on the left with "worst scar". The observer will be asked to mark on the line where they believe the scar "best fits". If the patient does not appear for their follow-up visit, a phone call will be made to the parent or guardian, who will be asked to report their satisfaction of the wound on a scale of 1 to 10, with 1 being "very unsatisfied" and 10 being "very satisfied".

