c) If the proposed study is a clinical trial where a drug, vaccine, device or other treatment is compared to a placebo group or comparison treatment group, what are the guidelines or endpoints by which early decisions regarding efficacy or lack of efficacy can be made? For example, it may be reasonable to stop enrollment on a study when efficacy has already been clearly demonstrated, to avoid unnecessary enrollments of additional subjects. Alternatively, it may be reasonable to stop enrollment when it is clear that efficacy will never be demonstrated, given the statistical power of the study as designed. Describe the guidelines that are in place to assist in making these determinations, if relevant to the proposed study.

On an ongoing basis, we will evaluate potential complications and if we identify serious complications related to the study group, we will consider study termination.

d) Describe how data analysis will be performed (statistical tests, methods of evaluating data) and indicate the smallest group/unit for which separate reporting will occur. For studies involving a questionnaire, if data and reliability information are available, please describe or provide references. For full board, unfunded studies describe sample size determination and power analysis. If none, please justify.

Differences between groups will be analyzed using the Student's t-test for independent samples. Proportions will be compared using chi-square and the z-test for independent proportions. A significance level of 0.05 will be used in all analysis. Since this is an equivalence trial, a non-inferiority average difference of 15mm with the cosmesis VAS scale will be considered clinically equivalent. Previous studies have determined that the minimal clinically important differences between two groups ranged from 10 to 15mm (4,15,16).

A sample size of 18 patients per group will be needed to provide a power of 90% with 0.05 alpha error to detect a 15mm difference in the VAS. A patient attrition rate of 40% is expected and with this considered, a total of 50 patients will be enrolled in order to power the study this will include the 20 patients already enrolled in the previous study (#23300).

Protocol Title: Conservative versus Suture Repair of Hand and Feet Lacerations in Children

Please save frequently

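### The call to families who miss a visit is described as asking only about satisfaction, so infection has no visible collection route for those children

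*Combined protocol and SAP*

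**What the plan says.** **Infection as an outcome.** Section 2(b) states "Secondary measures will be infection rates", followed by four other measures. The aim there is to save time, money and pain "while having no decrease in cosmetic satisfaction or infection rates". I read the last words as meaning no worsening of infection.

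**Where infection is assessed.** Section 3(b) asks the child to return at 10-14 days and continues: "The wounds will be evaluated for complications that were defined a priori as follows". Infection is then defined by a need for systemic antibiotics as judged by the treating attending physician. Dehiscence is defined by a need for further sutures or tissue adhesive.

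**Surveys.** For the 10-14 day visit: "Parents will fill out a follow-up survey at this visit". For the visit at 12-16 weeks: "The parent will fill out a second survey". Between the two stands a general sentence: "Follow up data will be obtained from the parent or care giver for all subjects in the form of a questionnaire".

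**Children who do not appear.** The only stated fallback is that "a phone call will be made to the parent or guardian, who will be asked to report their satisfaction of the wound", scored 1 to 10. This directly follows the description of the photograph rating. The other calls, on day 6-8 and in week 11, are for reminders and appointments.

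**Expected loss.** Section 3(d), in the sample-size paragraph, says "A patient attrition rate of 40% is expected".

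**The concern.** Every infection assessment that the text describes depends on the child coming back. The one contact designed for children who do not come back names satisfaction and nothing else. Followed as written, the plan may rest the infection comparison on attenders alone. Section 3(d) names chi-square and z-tests for proportions but gives no rule for children of unknown status.

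At stake is how far a statement that infection was no worse can be trusted. If attendance is unrelated to infection, an attenders-only comparison loses precision but is not biased. If it is related, the comparison may be biased in a direction that nobody can state. A reader of the results could not judge this without knowing how many children were never assessed.

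**Working it through.** **1. Is there a described route for a child who misses a visit?** Each candidate, set against that question:

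- Complication check, section 3(b): done at the 10-14 day return, so it needs attendance.
- First and second surveys, section 3(b): filled in at or described with the visits. Their content is not shown (section 16 lists them as attachments). The second may ask about earlier antibiotics, but that helps only children who attend it.
- The general sentence promising questionnaire data on all subjects, section 3(b): it goes on to describe the child returning, and gives no method for a child who does not.
- Missed-visit call, section 3(b): names a satisfaction score only, with no statement of which visit triggers it. If it is meant only for the 3-4 month visit, a missed early visit has no stated fallback.
- Ongoing review of complications or serious adverse events, sections 3(c), 9.9 and 9.11(b): no data source is named for absent children.
- Medical records, section 15 question 3: listed as a possible source. Which options were ticked cannot be seen, and no record review for infection is described.

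None of these is a described route for infection in an absent child.

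**2. How many early checks are there?** The lay summary in section 2(a) has returns at 7-10 and 14 days. Sections 2(c) and 3(b) have one return at 10-14 days. The passages conflict on the visits at which infection would be seen, and must be reconciled.

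**3. Does any stated figure measure the gap?**

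- The 40% in section 3(d) inflates 18 per group (36 in all) for a 15 mm difference on the cosmetic Visual Analogue Scale (VAS). The VAS is scored from photographs taken at 3-4 months, so the 40% probably refers to that visit. The enrolment of 50 is close to 36 x 1.40 = 50.4, whereas 36 / (1 - 0.40) = 60. That discrepancy is a separate matter and does not bear on this point.
- Continuing Review question 10 reports 9 withdrawals for non-return at 4 months, and question 7 gives 26 accrued: 9/26 = 34.6%. Attendance of these children at the early visit is not stated, and the losses are not split by arm.

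Neither figure gives the miss rate at the early visit.

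**4. Illustration of what unknown status costs.** Assume an equal split of the planned 50, so 25 per arm. With *a* known infections and *u* children of unknown status, the arm's rate lies between *a*/25 and (*a* + *u*)/25. The width is *u*/25, or 4 points per unknown child.

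| Assumed missed, each arm | *u* | Width, one arm's rate | Best-to-worst range, difference between arms |
|---|---|---|---|
| 0% | 0 | 0 points | ±0 points |
| 20% | 5 | 20 points | ±20 points |
| 40% | 10 | 40 points | ±40 points |

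The last column is centred on the difference in known events per 25. Its extremes require every unknown child in one arm to be infected and none in the other. If the 26 accrued were split equally (13 per arm, also an assumption), each unknown child would be worth 1/13 = 7.7 points.

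**5. Precision with complete data.** With no infections seen among *n* children, the one-sided 95% upper limit is 1 - 0.05^(1/*n*): 11.3% for *n* = 25 and 18.1% for *n* = 15. Even with nobody missing, an arm of this size cannot exclude a rate of about 1 in 10.

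**The case against.** The strongest reply is that the gap may lie in the file rather than in the plan. The visit sheets and both surveys are not reproduced, the protocol promises questionnaire data on all subjects, and the sentence about the call reads as a fallback for the cosmetic outcome, not as a full call script. An infection defined by physician-determined antibiotics could also be found in medical records without a study visit. This stands as a limit on the claim: the documents support *no visible route*, not *no route*. It does not remove the point, because no passage says how any of these would reach an absent child.

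A second reply is that the fix would not measure the defined outcome. A parent's report of antibiotics is not an attending physician's determination, and it could include preventive courses. This stands in part. It is why the question should ask about treatment of an infection, and why phone reports should be checked against records or shown separately. Dehiscence is not among the secondary measures in section 2(b), but section 3(b) defines it as a complication beside infection, so one question on it is reasonable.

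A third reply is that little of this can still be changed for this trial. That is correct and narrows the fix for children already enrolled.

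**Conclusion.** The point holds as a cheap improvement. In the visible text, infection is a secondary measure with no described collection route for children who miss their visits, and the trigger for the missed-visit call is unclear. The size of the gap is unknown because early-visit attendance is not stated. The 4 points per child rests on 25 per arm with an equal split, and is an illustration rather than an estimate.

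A reader might infer two stronger things:

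- **That about 40% of children, or 9 of the 26 accrued, have unknown infection status.** The documents do not support this. Both figures concern, or probably concern, the 3-4 month visit, and a child lost then may have been checked at the early visit.
- **That suture removal draws one arm back more than the other and so biases the comparison.** This is possible but not shown. Reminders, gift cards and free follow-up visits are described without distinction by arm, and losses are not reported by arm.

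The infection comparison is descriptive at this size even with complete data. The primary cosmetic outcome is not affected.

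**What to change.** **For a running or future trial of this design:**

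- State that either missed visit, early or late, triggers the call, and reconcile the early-visit schedule between sections 2(a), 2(c) and 3(b).
- Add two yes/no questions to the call, worded identically in both arms: were systemic antibiotics given to treat an infection of this wound, and was the wound later closed with stitches or adhesive? If the surveys already ask this, say so and reuse their wording.
- Where record access is approved, check reported antibiotics against the treating physician's record. Otherwise show phone-reported events separately from physician-determined ones.
- Report attendance by arm and visit. Count unreached children as unknown, not as event-free.

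The cost is two questions on a call already planned, plus an IRB amendment. The downside is that parent report is less certain than physician determination.

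**For children already enrolled:** the response to continuing review comment 3 says enrolment has ended. The Event History shows expiry on 06/21/2019 and withdrawal of the renewal on 09/30/2019, and the Board's comment requires data collection and analysis to stop during a lapse. Limit the change to stating, in any permitted report, attendance by arm, the infection denominator and the number of children of unknown status. This needs no new data.

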
Please save frequently

b) Describe any animal experimentation and findings leading to the formulation of the study, if

Protocol Title: Conservative versus Suture Repair of Hand and Feet Lacerations in Children

there is no supporting human data.

n/a

2. Purpose of the study

a) Provide a brief lay summary of the project in <200 words. The lay summary should be readily understandable to the general public.

The purpose of this study is to compare outcomes of 2 repair methods in simple (<2cm) hand and feet lacerations in the pediatric population (2-17 yrs). Our hypothesis is that there is no statistical difference in cosmetic outcomes between suture repair and non-repair of these injuries. This study has been performed in the adult population, but has not yet been done in children. We would like to be the first to show that conservative repair can be done in our pediatric population. The suture group will have their injuries repaired with non-absorbable sutures (nylon) which remain the gold standard in cosmetic repair of hands and feet. The conservative group will have identical cleaning and preparation of the wound, but the laceration will be covered with antibiotic ointment and sterile gauze without repair. Secondary outcome measure include patient satisfaction, infection rates, pain during repair, time of initial ED visit stay, and cost of supplies used in repair. Our patients will return in 7-10 and 14 days and in 3 months for evaluation. Wounds and scars will be evaluated at both 7-10 and 14 days and 3-4 months by both the researchers and the parents or care givers. A satisfaction survey will be administered to the parent or guardian. At 3-4 months, digital photographs of the healing lacerations will be graded for appearance by clinicians blinded to the repair method. The initial visit will be billed to their insurance and the follow-up visits will be free (non-registered).

Page numbers from a sponsor's protocol/grant may be referenced in 2b and 2c.

b) List your research objectives (specific aims & hypotheses of the study).

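### Time to return to normal activity falls to a generic t-test, which cannot use a child not yet back to normal at the last contact; a Kaplan-Meier and log-rank analysis would.

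*Combined protocol and SAP*

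**What the plan says.** - Section 2(b) gives the secondary list: "Secondary measures will be infection rates, pain scores, time to return to normal activity", followed by length of the ED visit and cost of supplies. The lay summary in 2(a) has a different list, "Secondary outcome measure include patient satisfaction, infection rates, pain during repair, time of initial ED visit stay" and cost of supplies, without return to normal activity. No section defines the outcome, its starting point, or the form on which it is recorded.
- Section 3(d) has two analysis sentences. One is general: "Differences between groups will be analyzed using the Student's t-test for independent samples". The other covers proportions: "Proportions will be compared using chi-square and the z-test for independent proportions". No time-to-event method appears.
- Section 3(b) sets the first follow-up at 10-14 days: "Parents will fill out a follow-up survey at this visit". At the same visit, "Children in the suture repair group will have their sutures removed". A second parent survey comes at 12-16 weeks; section 2(c) describes it as a repeat. The contents of the two surveys are not in the text available here.
- A family that misses a visit is telephoned. As described in 3(b), that call asks only for satisfaction on a 1-10 scale.
- On loss to follow-up, 3(d) says "A patient attrition rate of 40% is expected". The Continuing Review form (items 7 and 10) reports 9 withdrawals among 26 accrued, for not returning at 4 months.

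**The concern.** A time in days is not a proportion, so under 3(d) it can only go to the t-test. That test needs a number for every child. If a child is not back to normal at the last contact, only a lower bound is known, and the analyst must either leave the child out or enter the visit day as if it were the return day. Both remove the slow end of the distribution, and remove more of it from the slower arm, so the estimated difference moves towards zero.

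The gap between the surveys makes this possible. The second falls 84 - 14 = 70 to 112 - 10 = 102 days after the first, and a sizeable share of families is expected to be lost by then. Section 2(b) aims to show practical advantages of conservative care. An understated difference in return to normal activity would bear on that aim, though not on the primary cosmetic comparison.

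**Working it through.** **Plan's own figure.** There is none for this outcome. The 18 per group in 3(d) is for the cosmesis VAS. The 50 to be enrolled give 25 per arm, assuming equal allocation.

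**Assumptions, none from the documents.** Return times are exponential or Weibull. The slower arm is taken to be the suture arm. The first survey falls uniformly on days 10-14 (day 12 in the hand check). Tests are two-sided at 0.05; 3(d) does not state sidedness. The 60% giving a second survey is 1 - 0.40; the Continuing Review figure gives 1 - 9/26 = 65%. The second survey is assumed to record the return date.

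**Hand check: exponential, medians 5 v 10 days, visit at day 12.**

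- Full mean = median / ln 2: 7.21 and 14.43 days; difference 7.2.
- Not back at day 12, S = 2^(-12/median): 0.189 and 0.435.
- No second survey, unrecovered dropped. Mean = full mean - 12S/(1 - S): 7.21 - 2.81 = 4.41 and 14.43 - 9.25 = 5.18; difference 0.8.
- No second survey, visit day entered. Mean = full mean × (1 - S): 5.85 and 8.15; difference 2.3.
- 60% second surveys, the other unrecovered children dropped. Mean = [0.6 × full mean + 0.4 × (1 - S) × mean given return by day 12] / [0.6 + 0.4 × (1 - S)]:
  - median 5: (4.328 + 1.429) / 0.924 = 6.23
  - median 10: (8.656 + 1.170) / 0.826 = 11.90
  - difference 5.7
- 60% second surveys, visit day entered for the rest: 0.6 × 7.21 + 0.4 × 5.85 = 6.67 and 0.6 × 14.43 + 0.4 × 8.15 = 11.92; difference 5.2.

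**Simulation.** The t-test here drops unrecovered children.

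| Scenario | True difference (days) | After dropping (days) | t-test power | Log-rank power |
|---|---|---|---|---|
| Medians 2.5 v 5, shape 2, 18 per arm, no second survey | 2.7 | 2.5 | 94% | 97% |
| Medians 5 v 10, exponential, 25 per arm, 60% second surveys | 7.2 | 5.5 | 46% | 60% |
| Medians 5 v 10, shape 1.5, 25 per arm, 60% second surveys | 5.8 | 4.7 | 80% | 92% |
| Medians 5 v 10, exponential, 18 per arm, no second survey | 7.2 | 0.8 | 7-10% | 38-41% |
| Medians 5 v 10, shape 1.5, 18 per arm, no second survey | 5.8 | 1.4 | 20-22% | 76% |

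Ranges are the spread over repeated runs. The second row agrees with the hand figure of 5.7 within simulation error. In the first row only about 2% of the slower arm is not back by the visit (2^(-(12/5)²) = 0.018), so there is little to lose.

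If every child has a second survey that records the date (18 per arm, medians 5 v 10), the t-test estimates 6.9 days (exponential) and 5.8 days (shape 1.5), essentially the true values, with power 46% and 83%.

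Entering the visit day is kinder to power than to the estimate. In the fourth and fifth rows it gives 34-37% and 69% power, but reports 2.3-2.4 and 3.1 days against 7.2 and 5.8.

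**The case against.** A reader might infer that the item is asked only at the 10-14 day visit and that a real difference is therefore largely lost. The documents do not support this.

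- No section says at which visit the item is asked. Two surveys exist, their contents are not shown, and what is unseen cannot be counted as missing.
- The 12-16 week survey could supply late return dates. The 18 per group are children with a photograph from that same visit, so an analysis of 18 per arm with no second survey is an extreme case.
- Nothing in the plan chooses dropping over entering the visit day, and the latter keeps most of the power.
- No recovery times are given. For simple lacerations of at most 2 cm, few children may still be restricted at day 10-14. That children with sutures are held back until removal is conjecture.
- The t-test sentence is general and does not name this outcome.

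All of this stands, and it limits the size of the point. It does not remove it. The t-test is still the only stated method that fits, and there is still no rule for an unrecovered child. The second survey cannot be counted on for everyone, given the expected attrition, and the missed-visit call as described does not ask for a return date. Entering the visit day still understates how much sooner children recover.

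**Conclusion.** The point holds in a limited form. The plan has a time-to-event outcome, foreseeable incomplete times, and no method that can use them.

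The size is conditional:

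- **Almost none** if recovery is quick (medians 2.5 v 5 days, shape 2) or the second survey captures the date.
- **Moderate** with medians 5 v 10 days, 25 per arm and 60% second surveys: roughly a fifth to a quarter of the difference is lost (4.7 of 5.8 days; 5.5 of 7.2 days), and power is 12 to 14 points below log-rank.
- **Large** only if no second survey supplies the date, unrecovered children are dropped, and suture-arm recovery is slow. The documents do not show that this is the case.

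Log-rank power matched or exceeded that of the t-test that drops unrecovered children in the scenarios compared, so the change loses nothing where few times are incomplete. It does assume that loss to follow-up is unrelated to recovery, which should be stated. The point is minor: it concerns one secondary outcome and leaves the primary VAS analysis untouched.

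**What to change.** In 3(d), add that time to return to normal activity, counted from the ED visit, will be summarised by Kaplan-Meier curves and medians and compared by a log-rank test. A child not yet back to normal is censored at the last contact. The return date is taken from either survey or from the missed-visit call, where recorded. Keep the t-test for outcomes that are fully observed, such as length of the ED visit.

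In the same edit, state on which form the item is collected and bring the secondary lists in 2(a) and 2(b) into line. Section 2(a) puts the early follow-up at 7-10 and 14 days, and 2(c) and 3(b) at 10-14 days. These must be reconciled, because the visit day sets the censoring time.

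The cost is one sentence of analysis wording and, if the forms lack it, one item (back to normal or not, and the date) at existing contacts. No extra patients or visits are needed. The Comments section of the Continuing Review records that enrolment will not resume, so a new form item may come too late. The analysis wording can still be applied to data in hand wherever a return day, or a note that the child was not yet back, was recorded.

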Page numbers from a sponsor's protocol/grant may be referenced in 3b, 3c, and 3d.

b) Describe all the procedures, from screening through end-of-study, that the human subject must undergo in the research project, including study visits, drug treatments, randomization and the procedures that are part of standard of care. Specify which procedures are for research and which are standard of care. Please note: The box below is for text only. If you would like to add tables, charts, etc., attach those files in the Attachment section (#16).

Once a patient is deemed eligible, based on a review of his or her medical record, he/she will be approached by one of the pediatric emergency physicians to participate in the study. English-speaking parents or legal guardians will be asked to sign the consent form on behalf of the minor. Emancipated patients will be asked to sign for their own consent. A computer generated randomized allocations schedule will be determined upon opening of the sealed enrollment packets containing the pre-assigned repair method. Once consent has been obtained, initial demographic and injury data will be collected (see Data Collection Sheet, Appendix A). Patients will be ineligible for study enrollment if the digits' ligaments, bone or vascular supply is compromised by the injury or if the attending physician determines the depth of the wound is too deep, often greater than 0.5cm for healing by secondary intention.

The wound will be prepared by the usual and standard ED protocol. Lidocaine-epinephrine-tetracaine (LET) gel will be applied to the wound on presentation. The wound will be irrigated under tap water for 1-2 minutes and direct pressure applied to dry the wound. For patients in the suture repair group, the wound will have local infiltration with 1% lidocaine with epinephrine. Sutures used will be 5-0 nylon. Bacitracin ointment and sterile gauze will then be used to cover and dress the wound. In the conservative group, no local anesthesia will be used after irrigation. Bacitracin ointment and sterile gauze will be used to cover and dress the wound. Standardized wound care instructions will be given to patients prior to discharge (see Wound Care Instructions, Appendix B).

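### Section 3(d) names Student's t-test, which pools the variances, although the evaluable arms are likely to be unequal and nothing supports equal variances; pre-specifying Welch's test is a minor, cheap improvement.

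*Combined protocol and SAP*

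**What the plan says.** Section 3(d) gives one rule for continuous outcomes: "Differences between groups will be analyzed using the Student's t-test for independent samples". It adds "A significance level of 0.05 will be used in all analysis", without stating sidedness. There is no unequal-variance version, no variance check and no method for a confidence interval. The margin sentence reads "Since this is an equivalence trial, a non-inferiority average difference of 15mm with the cosmesis VAS scale will be considered clinically equivalent".

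On numbers, the same section plans 18 per group for 90% power to detect 15 mm. It says "A patient attrition rate of 40% is expected" and sets total enrolment at 50, of whom 20 come from an earlier study. No SD for the VAS is given, for either arm.

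On allocation, section 3(b) describes a computer-generated schedule in sealed packets. It states no ratio, block size or stratification; 1:1 is implied only by the per-group sample size.

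On treatment, section 2(c) says wounds are treated "by an attending physician, PEM fellow, or senior resident", and this covers every patient. Section 3(b) gives local infiltration and suturing to one arm only, and says of the other: "In the conservative group, no local anesthesia will be used after irrigation". Cleaning and dressing are shared.

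**The concern.** The pooled t-test averages the two sample variances with weights that favour the larger arm. If the variances differ and the arms are unequal, the standard error is biased. It is too small when the smaller arm is the more variable, and too large when the larger arm is. The error rate and the coverage of any interval move accordingly.

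The documents assure neither safeguard. Heavy loss without stated blocking makes unequal evaluable arms likely. Equal variances are not supported by any figure, and because only one arm undergoes infiltration and suturing, pain, time and supply cost may plausibly vary more there. The VAS is the primary outcome, and the same sentence governs the continuous secondary outcomes.

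**Working it through.** **Inputs from section 3(d):** 18 per group, 90% power, 15 mm, alpha 0.05, 50 enrolled, 40% loss. **Assumed:** normal data and SD ratios of 1.25, 1.5 and 2, because the plan gives no SD.

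**1. The plan's own figure.** The 18 per group cannot be reproduced without an SD, but it can be solved backwards. From n = 2(z₀.₉₇₅ + z₀.₉₀)²σ²/Δ², σ = 15 × √(18/2) / (1.960 + 1.282) = 45/3.242 = 13.9 mm (two-sided, normal approximation). With the t distribution it is 13.5 mm. With a one-sided 0.05 it is 15.1 to 15.4 mm. One common SD fits the figure, but this says nothing about whether the arms share it.

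**2. How unequal will the arms be?** Evaluable: 50 × 0.6 = 30.
- Given exactly 30 evaluable under simple randomisation, Binomial(30, 0.5): 18/12 or wider in 36% of trials and 20/10 or wider in 10%. Both directions are counted; a given arm is the smaller one in half of these, 18% and 5%.
- Letting the evaluable total vary as well (50 enrolled, independent 40% loss): 1.5:1 or wider in 29% under simple randomisation and 10% under a fixed 25:25 schedule; 2:1 or wider in 8% and 1%.
- On the Continuing Review form, 26 were accrued and 9 lost, leaving about 17, with no split by arm. (An IRB comment implies 18 followed and 9 not, total 27.) Of 17, an 11/6 or wider split occurs 33% of the time.

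**3. Why the pooled standard error goes wrong.** Let arm A have SD 1.5 and arm B SD 1. The true variance of the difference is 1.5²/n_A + 1/n_B. The pooled test on average estimates [((n_A−1)1.5² + (n_B−1))/(n_A+n_B−2)] × (1/n_A + 1/n_B).
- 12/18: true 0.1875 + 0.0556 = 0.2431; pooled (24.75 + 17)/28 × 0.1389 = 0.2071. SE ratio √(0.2071/0.2431) = 0.92, too small.
- 15/15: true 0.2167; pooled 1.625 × 0.1333 = 0.2167. SE ratio 1.00.
- 18/12: true 0.2083; pooled (38.25 + 11)/28 × 0.1389 = 0.2443. SE ratio 1.08, too large.

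**4. Error rates.** Simulation, 400,000 trials per cell, nominal two-sided 5%:

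| n, more variable arm / other arm | SD ratio | Pooled | Welch |
|---|---|---|---|
| 10/20 | 1 (equal) | 5.1% | 5.1% |
| 15/15 | 1.5 | 5.1% | 5.0% |
| 12/18 | 1.25 | 6.1% | 5.0% |
| 12/18 | 1.5 | 7.1% | 5.0% |
| 12/18 | 2 | 8.6% | 5.1% |
| 18/12 | 1.25 | 4.2% | 5.0% |
| 18/12 | 1.5 | 3.5% | 4.9% |
| 18/12 | 2 | 3.0% | 5.0% |

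At ratio 1.5, coverage of a pooled 95% interval is therefore 92.9% at 12/18 and 96.5% at 18/12.

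**5. Averaged over chance imbalance** (50 enrolled, 40% loss), at ratios 1.25, 1.5 and 2: pooled 5.1%, 5.3%, 5.8% under simple randomisation and 5.1%, 5.2%, 5.5% under fixed 25:25. Welch stays at 5.0% to 5.1%. With 26 accrued and 17 evaluable, simple randomisation gives 5.2%, 5.5%, 6.2%.

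**6. Cost of Welch when variances are equal** (SD 13.9 mm, 15 mm difference). Power, pooled against Welch: 88.3% and 88.2% at 18/18; 79.9% and 79.2% at 12/18; 76.9% and 75.0% at 10/20. The losses are 0.1, 0.7 and 1.9 points.

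**The case against.** The strongest reply is that no error has been shown, because unequal numbers alone do no harm: with equal SDs the pooled test stays at about 5% even at 10/20. Everything then rests on an SD ratio that the documents do not give. That stands.

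A reader might infer that only the suture arm's scar depends on the operator, so that its VAS must be the more variable. The documents do not support this. Section 2(c) applies the three grades to all patients, and nothing says that grade affects the scar. The opposite direction is equally arguable, since section 9 lists poor wound closure and scarring among the risks of conservative treatment. Even granting an operator effect in one arm only, on a base SD of 13.9 mm an added SD of 5 mm gives a ratio of √(13.9² + 5²)/13.9 = 1.06; 10 mm gives 1.23, and it takes 15 mm to reach 1.47. For the VAS, ratios near 1.06 to 1.25 are thus easier to defend than 2.

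Two further limits stand. The 20 children from the earlier study are not evidence of imbalance, because their split is not reported. And a reader might infer that pooling makes an equivalence claim too easy. The plan names a difference test and never says how the 15 mm is to be tested. If non-significance were read as no difference, a standard error that is too small would make that claim less often.

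What remains against the reply is that one trial is analysed with one split. The average of 5.1% to 5.8% is not the error rate given that split, and choosing Welch after seeing the split or the variances would be a data-driven choice.

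**Conclusion.** The point holds as a low-severity improvement, not as a demonstrated error in the plan. Unequal evaluable arms are likely on the plan's own loss rate, although how likely depends on an unstated randomisation scheme. Unequal variances are possible, and perhaps more plausible for pain, time and supply cost than for the VAS, but the documents do not show which arm is more variable, or that either is. If they do differ, with assumed ratios of 1.25 to 2, the pooled test's two-sided 5% error is about 6% to 9% at an unfavourable 12/18 split and about 3% to 4% at the reverse split. The average over chance imbalance is close to nominal. These figures assume normal data and loss unrelated to arm.

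**What to change.** In section 3(d), replace Student's t-test with Welch's unequal-variance t-test and its confidence interval, for the VAS and every other continuous outcome, fixed before the arms are compared.

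The cost is one phrase and no patients. If the variances are in fact equal, the price is the power loss in step 6 of the working, which is negligible with equal arms.

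This change leaves a larger gap in the same section open: the 15 mm margin still needs its own stated test or interval comparison, with sidedness and a choice between equivalence and non-inferiority. A Welch interval would be a suitable basis for that comparison, but naming it does not by itself make the comparison.
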